11.1 Primary Efficacy Endpoint and Analysis

The primary efficacy endpoint is defined as the change from baseline of the ADHD-RS-5 total score at Visit 6 (Week 4). Baseline ADHD-RS total score is defined as the last valid ADHD-RS-5 total score assessment prior to taking the first dose of double-blind investigational product, usually at Visit 2 (Week 0).

The primary efficacy analysis will be conducted on the FAS for the change from baseline for the ADHD-RS-5 total score, including all assessments from Visit 3 (Week 1) up to Visit 6 (Week 4). The primary efficacy endpoint will be analyzed by using the linear mixed-effects model for repeated measures (MMRM) with treatment group (SHP465 6.25 mg and Placebo), visit, age group (6-8 years vs. 9-12 years) and the interaction of treatment group with visit as factors, baseline ADHD-RS-5 total score as a covariate, and the interaction of baseline ADHD-RS-5 total score with visit adjusted in the model.

The REML (restricted maximum likelihood) method of estimation, which is default in SAS, will be utilized along with the Kenward-Roger method for estimating the covariance matrix and degrees of freedom. The model will use an unstructured covariance type.

The primary contrast of interest will be at Visit 6 (Week 4) for SHP465 6.25 mg compared with placebo.

The null and alternative hypotheses of the primary efficacy analysis are:

- Null hypothesis: There is no difference in mean change from baseline at Visit 6 (Week 4) in ADHD-RS-5 total score between SHP465 6.25 mg and placebo;
- Alternative hypothesis: There is a difference in mean change from baseline at Visit 6 (Week 4) in ADHD-RS-5 total score between SHP465 6.25 mg and placebo.

Descriptive statistics will be displayed for each treatment group and visit, as well as the least squares means and standard errors resulting from the MMRM. To compare SHP465 6.25 mg and placebo, the difference of least squares means, the corresponding 95% CI, and the effect size (Cohen's *d*) at Visit 6 (Week 4), defined as difference of the least squares means divided by the square root of the variance estimate at Visit 6 obtained from the SAS-estimated *R* matrix, will be displayed (Cohen, 1988). The p-value and effect size will only be presented for Visit 6 (Week 4). A corresponding line graph of the least squares means of change from baseline and associated 95% CI in ADHD-RS-5 total score by visit and treatment group will be presented.

The observed and change from baseline in ADHD-RS total score will be summarized at each applicable visit using the number of subjects, mean, SD, median, minimum, and maximum values.

The items in the ADHD-RS-5 will also be grouped into 2 subscales: hyperactivity/impulsivity (9 items for hyperactivity/impulsivity) and inattentiveness (9 items for inattentiveness). Each subscale will be analyzed using a similar model as the primary efficacy endpoint and summarized descriptively at each visit by treatment group. A corresponding line graph of the least squares means of change from baseline and associated 95% CI in ADHD-RS-5 subscale scores by visit and treatment group will be presented.

11.2 Key Secondary Efficacy Endpoint(s) and Analysis

The key secondary efficacy endpoint, CGI-I score, will be analyzed using the same analysis method (MMRM) as for the primary efficacy endpoint for the Full Analysis Set. The baseline CGI-S score will be used as the covariate. The primary contrast of interest will be at Visit 6 (Week 4) for SHP465 6.25 mg compared with placebo.

The CGI-I will be summarized descriptively at each applicable visit using the number of subjects, mean, SD, median, minimum, and maximum values.

As a supportive analysis, the key secondary efficacy measurement will also be analyzed using the proportion of subjects with an "improved" CGI-I measurement at Visit 6/ET (Week 4/ET). The CGI-I categories will be dichotomized into 2 categories; "very much improved" and "much improved" classified as "improved" (CGI-I score of 1 or 2) and all other assessed categories grouped together as "not improved" (CGI-I score of >2). If missing data exist at the Visit 6 (Week 4) visit, the visit will be imputed by carrying forward the last post-baseline observation value. The dichotomized CGI-I will be analyzed by comparing SHP465 6.25 mg and placebo on the FAS for the proportion of "improved" subjects using a Cochran-Mantel-Haenszel test stratified by age group and CGI-S value at baseline.

The observed and dichotomized CGI-I values will be summarized at each applicable visit using number of subjects and percentages as well.

A corresponding bar chart showing the percentage of subjects improved by visit and treatment group will be presented. CGI-I values and CGI-S values will be listed for FAS.

11.3 Adjustments for Multiplicity for the Primary and Key Secondary Endpoint

In order to protect the study-wide Type I error at the 2-sided 0.05 for testing across the primary and the key secondary hypotheses, the Fixed-Sequence Test procedure will be applied. The hypotheses will be tested in the order of the primary (ADHD-RS-5 Total Score) and then the secondary (CGI-I), if significant for the primary, each at the 2-sided 0.05 significance level. Both tests in the sequence are based on the MMRM.

11.4 **Sensitivity Analysis Based on Missing Not at Random Assumptions**

The primary efficacy analysis (MMRM) relies on the assumption that the missing data mechanism follows the MAR (missing at random) scenario. It is assumed that the probability of missing data is unrelated to the value of the variable, after controlling for other variables in the data. The likelihood-based MMRM analysis is considered an appropriate method for the statistical analysis under MAR assumptions.

The following 2 sensitivity analysis models will be used to examine robustness of the primary analysis results. The sensitivity analysis models assume different MNAR mechanisms and are within the pattern-mixture model framework.

Model 1 - Placebo multiple imputations

Rationale: The imputations are based on the distribution of placebo group responses over time. The underlying assumption is that a subject on SHP465 6.25 mg treatment with missing data follows the distribution of the placebo responses, i.e., the means and the intra-subject correlations based on the placebo responses will apply.

The model is implemented in 3 steps: 1. imputations, 2. analysis of complete data sets, and 3. inference. Sample SAS codes are provided in Section 22.

Step 1: Imputations

A total of 200 sets of posterior mean and co-variance estimates are extracted from the SAS MI procedure using the available non-missing placebo data. One hundred of the posterior sets will be applied to the SHP465 6.25 mg treatment group, the other 100 applied to the placebo group. One set of imputations for all missing values will be generated based on each variation of posterior estimates. All 100 sets for imputations within a treatment group will be ordered from 1 to 100, and combined between the SHP465 6.25 mg treatment group and placebo, for a total of 100 completely imputed data sets.

Step 2: Analysis of complete data sets

The primary endpoint will be analyzed for each of the 100 complete data sets with imputed data using an ANCOVA with treatment and age group as the factor and the baseline value as a covariate.

Step 3: Inference

The LS mean difference estimates will be averaged and the associated standard errors will be summarized based on within-imputation and between-imputation variance using the SAS MIANALYZE procedure to yield a final estimate with associated 95% CI and p-value.

Model 2 - Multiple imputations with penalties applied to dropouts

Rationale: The underlying assumption is that subjects who drop out perform worse than MAR by a penalty.

The model is implemented in 3 steps: 1. imputations and application of penalty, 2. analysis of complete data sets, and 3. inference. Sample SAS codes for steps 1a and 1b are provided in Section 22.

Step 1a: Imputations

Missing data will be multiply imputed for 100 times based on a treatment specific, multivariate normal distribution of the response over time using the SAS MI procedure with treatment in the BY statement. This step is based on the MAR assumption.

Step 1b: Application of Penalty

A penalty will then be applied to the multiply imputed values at Visit 6 (Week 4). The penalty will be a fraction of the estimated SD for the primary endpoint (the square root of the estimated element for Visit 6 of the co-variance matrix \mathbf{R} from the primary MMRM model): (0*SD), (0.25*SD), (0.75*SD), and (1*SD).

Step 2 (analysis of complete data sets) and Step 3 (inference) are the same as Steps 2 and 3 respectively for Model 1.

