As the primary efficacy analysis (MMRM) relies on the assumption that the missing data mechanism follows the MAR (missing-at-random) scenario, appropriate sensitivity analyses to examine the effect of data that are missing not at random and robustness on the results of the primary analysis will be conducted.

One sensitivity analysis model assumes that a subject on SHP465 6.25 mg treatment with missing data follows the distribution of the placebo responses, i.e., the means and the intra-subject correlations based on the placebo responses will apply. Another sensitivity analysis model will be performed under the assumption that subjects who drop out perform worse than MAR by a penalty. The details of the sensitivity analysis methods will be specified in the Statistical Analysis Plan (SAP).

The key secondary efficacy endpoint, CGI-I will be analyzed using the same analysis method (MMRM) as for the primary efficacy endpoint. The baseline CGI-S score will be used as the covariate. The primary contrast of interest will be at Visit 6 (Week 4) for SHP465 6.25 mg compared with placebo at the 2-tailed significant level of 0.05. Appropriate sensitivity analyses to explore the effect of data that are missing not at random on the results of the key secondary efficacy analysis will be specified in the SAP.

In order to protect the study-wide Type I error at the 2-sided 0.05 level for testing across the primary and the key secondary hypotheses, the Fixed-Sequence Test procedure will be applied. The hypotheses will be tested in order of the primary (ADHD-RS-5 Total Score) and then the key secondary (CGI-I), if significant for the primary, each at the 2-sided 0.05 significance level. Both tests in the sequence are based on the MMRM.

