9.9.1 Primary Efficacy Endpoint

The primary efficacy endpoint is defined as the change from baseline of the ADHD-RS-5 Total Score at Visit 6 (Week 4). The baseline ADHD-RS-5 Total Score is the last value obtained prior to taking the first dose of investigational product, usually at Visit 2.

The primary efficacy analysis will be conducted over the FAS for the change from baseline in the ADHD-RS-5 Total Scores, including all assessments from Visit 3 (Week 1) up to Visit 6 (Week 4). The primary efficacy endpoint will be analyzed by using the linear mixed-effects model for repeated measures (MMRM) with treatment group, visit, age group (6-8 years vs. 9-12 years), and the interaction of treatment group with visit as factors, baseline ADHD-RS-5 Total Score as a covariate, and the interaction of baseline ADHD-RS-5 Total Score with visit adjusted in the model. The primary contrast of interest will be at Visit 6 (Week 4) for SHP465 6.25 mg compared with placebo at the 2-tailed significance level of 0.05.

The null and alternative hypotheses of the primary efficacy analysis will be the following:

- Null hypothesis: There is no difference in primary endpoint mean change from baseline at Visit 6 (Week 4) in ADHD-RS-5 total scores between SHP465 6.25 mg and placebo
- Alternative hypothesis: There is a difference in primary endpoint mean change from baseline at Visit 6 (Week 4) in ADHD-RS-5 total scores between SHP465 6.25 mg and placebo.

SHP465-309

07 September 2017

As the primary efficacy analysis (MMRM) relies on the assumption that the missing data mechanism follows the MAR (missing-at-random) scenario, sensitivity analyses to examine the effect of data that are missing not at random and the robustness on the results of the primary analysis will be conducted. One sensitivity analysis model assumes that a subject on SHP465 6.25 mg treatment with missing data follows the distribution of the placebo responses, ie, the means and the intrasubject correlations based on the placebo responses will apply. Another sensitivity analysis model assumes that subjects who drop out perform worse than MAR by a penalty. The details of the sensitivity analysis methods will be specified in the SAP.

The observed and change from baseline ADHD-RS-5 Total Score will be summarized at each applicable visit using the number of subjects, mean, standard deviation, median, minimum, and maximum values.

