2.5.1 Sample Size Update

Following the SAP Section 2.5 and the protocol Section 9.6, a blinded interim analysis for sample size re-estimation was performed based on 47 randomized subjects as of 19 March 2018 (the interim cohort), among which 45 were in the FAS and 43 completed the study. Data of the interim cohort were extracted on 27 April 2018, after the collection of all their primary efficacy data.

The pooled standard deviation for Visit 6 (Week 4) used for sample size re-estimation was calculated using a pooled common variance that was estimated by using blinded cumulative primary efficacy data in the interim cohort. Then the final pooled standard deviation was

calculated as stated in Section 15 and Appendix 1. The interim analysis results showed a reestimated pooled standard deviation of 13.29 which is less than 14 and therefore an increase to the sample size was not required.

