5.4 Full Analysis Set

The Full Analysis Set (FAS) will consist of all subjects in the Safety Set who have had the baseline ADHD-RS-5 total score and at least 1 post-dose ADHD-RS-5 total score.

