22.2 Appendix 2 Sample SAS Codes

Mixed Model Repeated Measures (MMRM)

```
Proc mixed /* select derived data set */;
Class trt subjid visit agegp;
Model chg = trt visit agegp trt*visit base base*visit / ddfm=kr;
Repeated visit / subject=subjid type=UN;
/* LSMean, Estimate, and/or LSMestimate statement(s) */
/* Data output or object delivery statement(s) */
Run;
```

Mixed Model Repeated Measures (MMRM) for subgroup analysis

```
Proc mixed /* select derived data set */; Class trt
subjid visit;
Model chg = trt visit trt*visit base base*visit / ddfm=kr; Repeated visit /
subject=subjid type=UN;
by subgroup;
/* LSMean, Estimate, and/or LSMestimate statement(s) */
/* Data output or object delivery statement(s) */
Run;
```

Analysis of Covariance (ANCOVA)

```
Proc glm /* select derived data set */;
Class trt;
Model chg = trt agegp base/alpha=.05;
Lsmeans trt/stderr pdiff;
/* Data output or object delivery statement(s) */
Run;
```

Missing Not at Random (MMNAR) Sensitivity Analysis

Model 1: Placebo Multiple Imputation

```
* Step 1;
proc mi data=unimputed out=discard nimpute=200 seed=309 noprint;
    where treatment=1; * where 1 stands for placebo;
    var baseline chy1-chy4;
    mcmc outest=posteriors; * here we pick up the PLA posteriors;
run;

* 100 posteriors for the placebo, rest for SHP465 6.25 mg;
data posteriors(type=est);
    set posteriors;
```

```
if 1<=_imputation_<=100 then do; * assign placebo posteriors;
              treatment=1;
         end;
        if 100<_imputation_<=200 then do; * assign posteriors to SHP465 6.25 mg;
              treatment=2;
              _imputation_=_imputation_-100;
        end;
 run;
 proc sort data=unimputed;
    by treatment;
 run;
 proc mi data=unimputed out=imputed;
    by treatment;
    var baseline chy1-chy4;
    mcmc inest=posteriors; * here we use the placebo posteriors;
 run;
 * Step 2;
data endpoint;
    set imputed;
    endpoint=chy4;
run;
 proc sort data=endpoint;
    by _imputation_;
 run;
 proc glm data=endpoint;
    by _imputation_;
    class treatment agegp;
    model endpoint = baseline treatment agegp / solution;
    Ismeans treatment;
    estimate 'SHP465 6.25 mg vs placebo' treatment -1 1;
    ods output estimates=est;
 run;
 * Step 3;
 proc sort data=est;
    by label_imputation_;
 run;
 proc mianalyze data=est;
    by label;
    modeleffects estimate;
    stderr stderr;
 run;
```

Protocol SHP465-309

Model 1.

Model 2: Multiple Imputations with Penalties Applied to Dropouts

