* Note: dataset "unimputed" has one row per subject, repeated measures are structured in columns; * Step 1; data unimputed; set unimputed; missing=(Chy4 =.); run; proc sort data=unimputed; by treatment; run; proc mi data=unimputed out=imputed nimpute=&nimpute seed=309 noprint; by treatment; var baseline chy1-chy4; run; %let SD=10; * This will be replaced by the estimated SD[chy5] from the MMRM co-variance matrix R (use R or RCORR option in REPEATED statement under PROC MIXED); %let penalty=0.25*&SD; * Repeat this step for various values (0.25, 0.5, 0.75 and 1) as per SAP; data imputed; set imputed; if missing then chy4=chy4+ &penalty; * + or -, depending on the measure; run; * Step 2 (analysis of completed data sets) and Step 3 (inference) are the same as Steps 2 and 3 respectively for

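### Model 2 puts the same dropout penalty on both arms, so its estimate moves only with dropout imbalance; an SHP465-only version would be a cheap addition

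*SAP*

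**What the plan says.** SAP Section 11.4 plans two missing-not-at-random analyses.

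- **Model 1** imputes from the placebo distribution: "The underlying assumption is that a subject on SHP465 6.25 mg treatment with missing data follows the distribution of the placebo responses". It has no severity parameter.
- **Model 2** first imputes under MAR, separately by arm. Then, in Step 1b, "A penalty will then be applied to the multiply imputed values at Visit 6 (Week 4"). The penalty is a multiple of the Visit 6 residual SD from the primary model.

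The Model 2 code in SAP Appendix 2 flags anyone whose Week 4 change is missing and then runs `"if missing then chy4=chy4+ &penalty;"`, with no condition on treatment. The protocol names no arm either. Its synopsis says: "Another sensitivity analysis model will be performed under the assumption that subjects who drop out perform worse than MAR by a penalty". Section 9.9.1 says: "Another sensitivity analysis model assumes that subjects who drop out perform worse than MAR by a penalty".

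Step 2 of both models is an ANCOVA with treatment, age group and baseline. SAP Section 11.5 reuses both models for CGI-I.

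The penalty grid differs within the SAP. Section 11.4 lists 0, 0.25, 0.75 and 1 SD. The code comment lists 0.25, 0.5, 0.75 and 1 SD.

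**The concern.** A graded penalty is most useful when it shows how far SHP465 dropouts could fall below MAR before the conclusion changes. A penalty common to both arms does not show this, because whatever is added on one arm is offset on the other in proportion to the missing shares. A Model 2 series that stays flat may mean only that dropout was balanced. A series in which the drug effect grows with the penalty may mean only that placebo lost more subjects. Either could be reported as robustness. The same applies to CGI-I.

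**Working it through.** **Inputs.** Difference 11.9 and SD 14 (SAP 2.5). Interim pooled SD 13.29 (SAP 2.5.1). Interim cohort of 47 randomized, "among which 45 were in the FAS and 43 completed the study". Model 2 can impute only FAS members, that is, subjects "who have had the baseline ADHD-RS-5 total score and at least 1 post-dose ADHD-RS-5 total score".

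**The plan's own figure.** The SAP gives none for the Model 2 shift. Its sample-size inputs do reproduce: 26 per arm, difference 11.9, SD 14, two-sided 0.05 gives 85.2% power by the noncentral t, against 85% stated.

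**Formula.** Let M = 1 if Week 4 is missing. Model 2 replaces Y by Y + k × SD × M. Least squares is linear in Y, so in every imputed data set, and in their average, the treatment estimate (SHP465 minus placebo; negative favours SHP465) moves by k × SD times the treatment coefficient from regressing M on the same covariates. With m missing of n per arm:

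- as written: shift ≈ k × SD × (m_SHP/n_SHP − m_pbo/n_pbo)
- SHP465 only: shift ≈ k × SD × m_SHP/n_SHP

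**At interim missingness.** 45 − 43 = 2. Assume both lack a Week 4 value, all 43 completers are in the FAS, and there are 45/2 = 22.5 per arm. Then 13.29 × 2/22.5 = 1.18 and 13.29 × 1/22.5 = 0.59. The split by arm is not given.

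| Missing (SHP465, placebo) | 1 SD, as written | 1 SD, SHP465 only |
|---|---|---|
| 0, 2 | −1.18 | 0 |
| 1, 1 | 0 | +0.59 |
| 2, 0 | +1.18 | +1.18 |

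For k = 0.25, 0.5, 0.75 and 1, the largest shift is 0.30, 0.59, 0.89 and 1.18. As a share of the planned difference, 1.18/11.9 = 10%.

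**Higher missingness.** At 15% dropout, 9 of 60 leave. If about half leave before any post-dose score (interim: 2 of 4 non-completers were outside the FAS), about 4 of 56 are missing, with 28 per arm. Each missing subject then carries 13.29/28 = 0.47 points at 1 SD:

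| Missing (SHP465, placebo) | As written | SHP465 only |
|---|---|---|
| 1, 3 | −0.95 | +0.47 |
| 2, 2 | 0 | +0.95 |
| 3, 1 | +0.95 | +1.42 |

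If instead a full 15% of each arm were in the FAS without Week 4, SD 14 gives 14 × 0.15 = 2.1 points for SHP465 only and 0 as written.

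**Simulation check of the formula** (30 per arm, SD 14, assumed within-subject correlation 0.6, 600 trials, 20 imputations, Rubin's rules).

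- With 4 missing in each arm, the both-arm estimate was −12.02 with no penalty and −12.03 at 1 SD, while the SE rose from 3.87 to 4.07. SHP465 only gave −10.16 (formula: −12.02 + 14 × 4/30 = −10.15).
- With 3 SHP465 and 6 placebo missing, the both-arm estimate went from −11.78 to −13.18 (formula: −11.78 − 14 × 3/30 = −13.18), in the drug's favour. SHP465 only gave −10.38.

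**How severe is Model 1?** An SHP465 dropout keeps his or her own earlier scores, but Week 4 is predicted with placebo parameters. Assume equal correlation ρ between baseline and all visits, j visits observed, and w_i = the fraction of the Week 4 effect present at Week i. The departure from MAR, in SDs, is then

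(Δ/SD) × [1 − ρ/(1 + jρ) × Σ w_i, i = 1 to j].

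Take ρ = 0.6, Δ/SD = 11.9/13.29 = 0.895, and last visit at Week 1, 2 or 3 with equal weight:

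- constant effect: brackets 0.625, 0.455, 0.357; mean 0.479; severity 0.43 SD
- linear build-up to Week 4: brackets 0.906, 0.795, 0.679; mean 0.793; severity 0.71 SD (0.81 if the last visit is Week 1)
- true difference 8 (assumed), constant effect: 8/13.29 × 0.479 = 0.29 SD

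So Model 1 applies one severity, somewhere around 0.3 to 0.8 SD, which scales with the observed effect and its time course.

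**The case against.** The strongest reply is that nothing is wrong. The protocol says dropouts do worse than MAR and names no arm, and the SAP implements that. Lack of efficacy is a listed reason for discontinuation (Protocol 4.4.2), so penalising placebo dropouts is plausible, and a gain for SHP465 when placebo loses more subjects follows from the stated assumption. This stands: a reader might infer a coding error or a departure from the protocol, and the documents support neither.

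A reader might also infer that no planned analysis works against SHP465. Model 1 does. Nor can one say that Model 1 stops well short of 0.75 SD; that depends on a correlation and time course the documents do not give. What remains is that the SHP465-directed departure is not graded.

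The misreading is also partly preventable. Visit completion by arm (SAP 6) and numbers of subjects by arm and visit (SAP 11.1) are already planned, and the SHP465-only shift can be approximated by hand. That is true for the point estimate, but not for the SE, interval and p-value.

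Finally, the value may be low. With very few SHP465 values missing, even a large penalty moves little. This stands, and it sets the weight of the point.

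**Conclusion.** The point holds as a low-priority improvement. As written, Model 2's expected estimate responds to dropout imbalance, not to how badly SHP465 dropouts did. Under balance only the SE changes, and under heavier placebo loss a larger penalty favours the drug.

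The expected size is small: at interim missingness, −1.2 to +1.2 points as written and 0 to 1.2 points for SHP465 only, at 1 SD. This is unlikely to change a conclusion near the planned 11.9 points unless the result is borderline.

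The figures rest on the two interim FAS non-completers lacking Week 4, an unknown split by arm, and SD 13.29, which slightly overstates the residual SD the SAP would use. The count could go either way: an early-termination assessment can fill the next visit (SAP 19.3), and scores taken more than 2 days after the last dose are not analysed (SAP 11). The 4-missing case extrapolates from four interim non-completers.

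One might infer a serious threat from the simulated share of significant results, which with 4 of 30 missing per arm fell from 87% to 69% under an SHP465-only 1 SD penalty (85% as written). That is illustrative only: 4/30 is 13% missing per arm, against 2/45 = 4.4% in the interim FAS.

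**What to change.** Keep Model 1 and the both-arm Model 2 as pre-specified, and make these additions.

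- Add a version of Step 1b that penalises SHP465 imputed values only: `if missing and treatment=2`. The Model 1 code already uses 2 for SHP465 (its comment there reads "assign posteriors to SHP465 6.25 mg").
- Do the same for CGI-I, with the Visit 6 SD from the CGI-I model.
- Use one grid in text and code: 0, 0.25, 0.5, 0.75 and 1 SD. The omission of 0.5 SD from the text needs reconciling in any case.
- Show the number of imputed Week 4 values by arm beside the results.

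The cost is one code condition, a repeat run for each endpoint, one or two SAP sentences and a small table addition, with no new data. To count as pre-specified, it must be in place before unblinding. The downside is that the sensitivity result may look slightly less favourable, and it may add little if few SHP465 values are missing.

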11.5 Other Sensitivity Analysis

Other sensitivity analyses will be used to examine 2 different issues in this study:

- 1. Robustness of the key secondary efficacy analysis (MMRM) results for the CGI-I will be examined using the 2 sensitivity analysis models described in Section 11.4.
- 2. Impact of potential unblinding of 10 subjects due to unintentional urine drug screen performed erroneously after the final on-treatment assessments (see Section 18.1 for further details)

To evaluate whether the potential unblinding modified the efficacy results, sensitivity analyses of the primary efficacy (ADHD-RS-5 total score) and key secondary efficacy (CGI-I) analyses will be performed, in which these 10 subjects will be excluded from the FAS. The results between the primary and key secondary efficacy analyses and the sensitivity analyses will be examined.

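### Does the pooling step of the dropout-penalty analysis (Model 2) need a small-sample degrees-of-freedom correction, and its imputation an age-group term?

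*SAP*

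**What the plan says.** SAP 11.4 sets out two sensitivity analyses for data missing not at random. In Model 1, each of 100 completed data sets is analysed "using an ANCOVA with treatment and age group as the factor and the baseline value as a covariate". The estimates and standard errors are then combined "using the SAS MIANALYZE procedure to yield a final estimate with associated 95% CI and p-value". Model 2 imputes under missing-at-random within each arm and adds a penalty to imputed Week 4 values. The penalty is a multiple of the SD, starting at zero in the SAP text. For the remaining steps, "Step 2 (analysis of complete data sets) and Step 3 (inference) are the same as Steps 2 and 3 respectively for Model 1".

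The only pooling code, in SAP 22.2, opens with "proc mianalyze data=est". It reads an estimate and a standard error and has no EDF option. The Model 2 imputation code there runs "by treatment; var baseline chy1-chy4; run", so age group is not among its variables.

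The primary mixed model in SAP 11.1 includes age group and is fitted "along with the Kenward-Roger method for estimating the covariance matrix and degrees of freedom". SAP 11.5 extends both sensitivity models to CGI-I, which is "examined using the 2 sensitivity analysis models described in Section 11.4". On missing data, SAP 2.5.1 reports 47 randomised children at the interim, "among which 45 were in the FAS and 43 completed the study".

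**The concern.** At zero penalty, Model 2 is a missing-at-random analysis of the primary endpoint, so a reader will set it beside the primary result. The primary result uses a small-sample reference distribution and Model 2 by default does not. With the same estimate and standard error, a small-sample p-value between 0.050 and about 0.056 would appear as p<0.05 at the start of the penalty series. The series would then begin from a slightly flattering point. The age-group omission adds that the imputation does not condition on everything in the primary model. At stake is the comparability of a robustness check, for ADHD-RS-5 and for CGI-I.

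**Working it through.** **Plan's own figures.** SAP 2.5 gives 26 completers per group for 85% power (difference 11.9, SD 14, two-sided 0.05). The noncentral t gives 85.2%. For 15% dropout, 52 × 1.15 = 59.8, which gives the stated 60 (52/0.85 would be 61.2). The plan states no df or critical value for Model 2, so there is nothing further to reproduce.

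**Default pooling.** With m = 100 imputations and fraction of missing information g, Rubin's df = (m − 1)/g² = 99/g². The documents do not give g, so it is an assumption, taken from 0.02 to 0.15:

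- g = 0.02: 247,500 df
- g = 0.044 (2 of 45 interim FAS children): 51,136 df
- g = 0.15: 4,400 df

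The critical value is 1.960 to 1.961 throughout.

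**Small-sample pooling (Barnard-Rubin).** The complete-data df are v0 = N − 4 (intercept, treatment, age group, baseline). The observed-data df are (1 − g) × v0(v0 + 1)/(v0 + 3), combined harmonically with Rubin's df. At N = 57 and g = 0.044:

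- v0 = 53, and 53 × 54/56 = 51.1
- 51.1 × 0.956 = 48.9, or 48.8 after combining
- critical value 2.010, and 2.010/1.960 = 1.025

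Over g from 0.02 to 0.15 the critical value is 2.006 to 2.014 at N = 60 and 2.009 to 2.017 at N = 57. The default intervals are therefore about 2.3 to 2.9% too narrow.

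**In scale points.** With 28 per arm and SD 14, SE = 14 × √(2/28) = 3.74 and the half-width is 1.96 × 3.74 = 7.3. The difference is 0.050 × 3.74 = 0.19 points. With the interim SD of 13.29 it is 0.18.

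**How many values are missing.** If the interim pattern holds, (45 − 43)/47 × 60 = 2.6 FAS children lack Week 4 data, about one per arm. At the planned 15%, 0.15 × 28 = 4.2 per arm.

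**Null rejection rate, Model 2 at zero penalty.** These simulations used 28 per arm, 100 imputations by arm, ANCOVA and Rubin pooling. They assumed SD 14, between-visit correlation 0.3 or 0.6, and random monotone dropout. Each cell had 20,000 to 120,000 runs (Monte Carlo SE 0.06 to 0.15 points). Ranges cover the correlations and repeat runs.

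| Missing per arm | Default | With EDF = N − 4 |
|---|---|---|
| 1 | 5.3–5.5% | 4.7–4.9% |
| 2 | 4.7–5.3% | 4.1–4.7% |
| 3 | 4.8–5.0% | 4.2–4.4% |
| 4 | 4.6–4.8% | 4.0–4.2% |

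A smaller run with 60 children gave 4.9% against 4.4% at 5% dropout, and 4.5% against 4.0% at 15% (1,500 and 3,000 runs, SE 0.4 to 0.6 points). Imputing separately by arm from few children already makes the pooled analysis slightly conservative, and this offsets the looser critical value. Model 1 without the correction gave 4.8% with one missing per arm and 3.5% with three, so it shows no inflation.

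**Age group.** Assume an age effect of 3 to 5 points, equal-sized strata, and all missing children from one stratum. Imputation then misses by half the effect, less what earlier visits recover. With k earlier visits and correlation ρ, the fraction left is 1 − kρ/(1 + (k − 1)ρ).

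- Largest: 3/28 × 2.5 × 0.70 (k = 1, ρ = 0.3) = 0.19 points
- Smallest: 1/28 × 1.5 × 0.18 (k = 3, ρ = 0.6) = 0.01 points

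**The case for a change.** The strongest case for changing the plan is that the correction costs one option and one sentence, and that the missingness indicated by the trial's own interim counts is the row where it helps. With one missing value per arm, 5.3 to 5.5% falls to 4.7 to 4.9%, and the larger simulations are precise enough to show this. The sample code could be completed sensibly by the programmer, but the SAP text does not ensure it.

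That row stands. It rests, however, on 2 of 45 children and on equating completion with an analysable Week 4 score. SAP section 11 drops assessments taken more than 2 days after the last dose, which can add missing values. SAP 19.3 moves an early-termination visit to the next nominal visit, which can remove some. At two per arm the default is already close to nominal, and beyond that the correction overshoots.

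The like-for-like argument is also only partly right. The mixed model fits one covariance matrix to both arms, whereas Model 2 imputes by arm and pools a single-visit ANCOVA. A matching df would not make them the same analysis. Correcting Model 2 alone would also break the SAP's rule that the two models share their analysis and inference steps.

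**Conclusion.** No change is needed. The missing df value is real as documented, and its effect is about 0.05 on the critical value, or 0.2 ADHD-RS-5 points in half-width. It lifts the rejection rate above 5% by at most about half a percentage point, and clearly so only with about one missing Week 4 value per arm. Toward the dropout the SAP planned for, the default lies nearer 5% than the corrected version does, so the correction is not shown to be better overall. The age-group omission is worth 0.01 to 0.19 points under the assumptions used and would change no result. Both confirmatory tests are on the mixed model (SAP 11.3), and Model 2 carries no pass or fail rule at any penalty. An analyst could set the df in the final program without contradicting the SAP, and no conclusion would turn on it. These figures rest on assumed correlations, random dropout and the stated range of missing information, none of which the documents give.
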